9.2 Data Sets Analyzed

All eligible patients who receive at least one dose of telatinib (the Safety Population) will be included in the safety analysis.

All patients who receive at least one dose of telatinib will be included in the efficacy analysis. Patients who drop before disease progression will be right censored.

9.3 Data Analyses/Study Endpoints

9.3.1 Efficacy Analysis

The primary analysis will be based on an intention to treat approach and will include all subjects entered into the study at Cycle 1 Day 1.

The primary efficacy endpoint will be Progression-Free Survival. For each cohort, the logrank test will be used to test the null hypothesis that the median PFS is less than or equal to 2 months for the AGC cohort and 4.9 months for the HCC cohort under exponential distribution assumption for time to progression. If this assumption is violated, bootstrap methods will be used to construct a 95% confident interval for the median.

Kaplan-Meir (KM) curves with 95% confidence bands will be constructed for PFS of each cohort. For the secondary endpoints, exact 95% confidence intervals for ORR, DCR will be constructed and KM curves for OS will be reported. For the exploratory objectives, 95% confidence intervals for change in mean values of biomarkers such as inflammatory cytokines, plasma metabolites will be constructed.

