ECG	Electrocardiogram
ECOG	Eastern Cooperative Oncology Group
HCC	Hepatocellular carcinoma
HRPP	Human Research Protections Program
INR	International normalized ratio
IV (or iv)	Intravenously
MTD	Maximum Tolerated Dose
ORR	Overall Response Rate
OS	Overall Survival
PBMCs	Peripheral Blood Mononuclear Cells
PD	Progressive Disease
PFS	Progression Free Survival
PO	per os/by mouth/orally
PR	Partial Response
PT	Prothrombin time
SAE	Serious Adverse Event
SD	Stable Disease
ULN	Upper limit of normal
WBC	White Blood Cells
WOCBP	Women of childbearing potential

STUDY SCHEMA

Title	A Phase II Study Evaluating Safety and Efficacy of Telatinib in Combination with Keytruda in Subjects with Advanced Stomach and Gastroesophageal Junction Cancers or Hepatocellular Carcinoma	
Protocol Number	IIT2020-11-[name]-TELAT	
Phase	Phase II	
Methodology	Single arm, open label study with two parallel cohorts	
Study Duration	Approximately 30 months (anticipated accrual duration 12 months, with up to an estimated 12 months on-treatment and up to an estimated 6 months follow-up) Stopping rules for safety will be followed.	
Study Center	Cedars-Sinai Medical Center and affiliates	
	Primary:	
	The primary objective is to assess progression-free survival (PFS) in subjects with advanced gastric cancer or HCC receiving telatinib 900 mg BID in combination with Keytruda.	
	Secondary:	
	The secondary objectives are to assess:	
Objectives	Overall response rate (ORR), Disease Control Rate (DCR), Overall survival (OS), and Safety	
	Exploratory:	
	Time to Progression (TTP)	
	Change in inflammatory cytokines	
	Change in plasma metabolites	
	Change in immune cell profile	
	Change in stool microbiome	
	21 subjects with advanced gastric cancer	
Number of Subjects	24 subjects with advanced hepatocellular carcinoma	
Diagnosis and Main Inclusion Criteria	Adult subjects with advanced gastric cancer or HCC who are indicated for Keytruda	
Study Product(s), Dose,	Telatinib 900 mg (3 x 300 mg tablets) will be administered orally, twice daily.	
	Keytruda will be administered IV 200 mg every 3 weeks.	
Duration of administration	Until disease progression, intolerable toxicities, or withdrawal of consent	
Statistical Methodology Gastric cancer: PFS will be compared to KEYNOTE-059 with a endpoint of improvement in PFS from 2.0 months to 4 months. HCC: PFS will be compared to KEYNOTE-224 with a primary e of improvement in PFS from 4.9 months to 10 months		

STUDY SUMMARY

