With the development of new chemotherapies or targeted agents which are potentially more effective and less toxic, many patients can still maintain a good general condition after failing second-line therapies. According to previous studies, around 20–90% patients were able to continue active third-line or further lines of treatment. Established third-line therapies include chemotherapies: irinotecan, taxane and TAS-102, tyrosine kinase inhibitors: apatinib and regorafenib, and immune-checkpoint inhibitors (CPIs): nivolumab and pembrolizumab. Given the expanding options for third-line therapies, there is an unmet need for clinicians to individualize treatment.

Pembrolizumab is a humanized anti-PD-1 monoclonal antibody. In the KEYNOTE-059 Cohort 1, a multicenter, open-label, single-arm phase II trial conducted at 67 sites in 17 countries, 259 patients (after failing two or more lines of chemotherapy including cisplatin and 5FU; patients with Her-2 positive tumors must have received treatment with trastuzumab) received a fixed dose of 200mg pembrolizumab in a 3-weekly cycle [12]. Pembrolizumab showed an objective response rate of 11.6% (95% CI 8.0–16.1%), with complete response of 2.3% (95% CI 0.9–5.0%). The response rate was higher in the patients with PD-L1 positive tumors (PD-L1-positive versus PD-L1-negative: 15.5% versus 6.4%). A total of seven (4%) tumors were microsatellite instable (MSI)-high (H) and the response rates were higher, with an overall response rate of 57,1%. Median PFS was 2.0 months and median OS was 5.6 months. Based on this result, the Food and Drug Administration (FDA) has approved pembrolizumab as the third line treatment for PD-L1-positive gastric adenocarcinoma. Adverse events (AE) of any grade was reported in 60.2% of patients receiving pembrolizumab. The most common any-grade AEs were fatigue, pruritis, rash, hypothyroidism, decreased appetite, anemia, nausea, diarrhea and arthralgia. Grade \geq 3 treatment-related AEs occurred in 17.8% patients, with more common AEs including anemia, fatigue and diarrhea. Overall, 17.8% of patients experienced at least one immune-mediated AE of any grade; the most common were hypothyroidism (8.9%), hyperthyroidism (3.5%) and colitis (2.3%).

This study aims to explore the clinical safety and efficacy of combination of Telatinib, a potent oral inhibitor of VEGFR2 tyrosine kinase, and Pembrolizumab within the 3rd line and after treatment of locally advanced and metastatic gastric cancer

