4.1 Inclusion Criteria

- 4.1.1 Diagnosis:
 - **4.1.1.1** Histologically confirmed gastric/esophagealgastric adenocarcinoma, recurrent, locally advanced or metastatic, PD-L1-positive disease (CPS ≥1), progressed on at least two prior lines of therapy and/or discontinued second line therapy for intolerance, indicated for Keytruda therapy.

- **4.1.1.2** Hepatocellular carcinoma, with diagnosis confirmed by histologic or cytologic analysis or clinical features according to the American Association for the Study of Liver Diseases criteria for patients with cirrhosis, unresectable disease not amenable to locoregional therapy with disease progression after at least one prior line of systemic therapy or discontinued first line therapy for intolerance.
- **4.1.2** At least 1 measurable metastatic lesion that has not been irradiated. The lesion will be measured according to Response Evaluation Criteria in Solid Tumors (RECIST 1.1), and be documented by radiological evaluation within 28 days prior to registration. *For subjects with locally advanced disease:* at least one measurable lesion that has not been irradiated, documented by radiological evaluation within 28 days prior to registration.
- **4.1.3** Any prior radiation therapy must be completed at least 28 days prior to C1D1.
- 4.1.4 Eighteen years of age or older.
- **4.1.5** Eastern Cooperative Oncology Group (ECOG) performance score of 0, 1, or 2.
- **4.1.6** Adequate bone marrow, liver, and renal function as assessed by:
 - **4.1.6.1** Hemoglobin ≥ 9.0 g/dL
 - 4.1.6.2 Absolute neutrophil count (ANC) ≥1500/mcL
 - **4.1.6.3** Total bilirubin \leq 3.0 times the upper limit of normal (ULN)
 - **4.1.6.4** Alanine aminotransferase (ALT) and aspartate aminotransferase (AST) \leq 5.0 x ULN in the presence of liver metastasis; ALT and AST \leq 3.0 x ULN in the absence of liver metastasis
 - **4.1.6.5** International normalized ratio for prothrombin time (PT/INR) \leq 1.5 and activated partial thromboplastin time (aPTT) \leq 1.5 x ULN. The use of full-dose oral or parenteral anticoagulants is permitted as long as the INR or aPTT is within therapeutic limits (according to the medical standard in the institution) and the subject has been on a stable dose of anticoagulants for at least two weeks before C1D1.
 - **4.1.6.6** Serum creatinine ≤ 1.5 times the ULN AND/OR

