9.0 STATISTICAL CONSIDERATIONS

9.1 Sample Size

For the AGC cohort, the median PFS in the KEYNOTE-059 trial (Fuchs et al. 2020) is 2.0 months. Assuming an accrual time of 12 months and 6 months follow-up, 21 patients are needed to improve median PFS from 2 months to 4 months or HR = 0.5 with 80% power using a two-sided one sample log-rank test at the 0.05 level of significance. Time to progression was assumed to follow an exponential distribution.

For the HCC cohort, the median PFS in the KEYNOTE-224 trial (Zhu et al. 2018) is 4.9 months. Assuming an accrual time of 12 months and 10 months follow-up, 24 patients are needed to improve median PFS from 4.9 months to 10 months or HR = 0.49 with 80% power using a two-sided one sample log-rank test at the 0.05 level of significance. Time to progression was assumed to follow an exponential distribution.

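### The gastric null median of 2.0 months comes from a cohort that included PD-L1-negative patients, but this trial enrols only CPS ≥1 patients, and the plan does not justify the benchmark

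*Combined protocol and SAP*

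**What the plan says.** The study schema sets the benchmark: "PFS will be compared to KEYNOTE-059 with a endpoint of improvement in PFS from 2.0 months to 4 months". Section 9.1 sizes the cohort on it: "21 patients are needed to improve median PFS from 2 months to 4 months or HR = 0.5 with 80% power", using a two-sided one-sample log-rank test at 0.05, exponential times, 12 months of accrual and 6 months of follow-up. Section 9.3.1 makes the same figure the null: the test is to "test the null hypothesis that the median PFS is less than or equal to 2 months for the AGC cohort".

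Section 1.1.1 gives the source, a 259-patient single-arm cohort on pembrolizumab alone: "Median PFS was 2.0 months and median OS was 5.6 months". The same paragraph shows that the cohort was mixed for PD-L1: "The response rate was higher in the patients with PD-L1 positive tumors (PD-L1-positive versus PD-L1-negative: 15.5% versus 6.4" per cent, with 11.6% responding overall. No PFS is given by PD-L1 status.

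Section 4.1.1.1 restricts this trial's gastric cohort to "recurrent, locally advanced or metastatic, PD-L1-positive disease (CPS ≥1), progressed on at least two prior lines of therapy" (or discontinued second-line therapy for intolerance). No section adjusts the 2.0 months for this restriction or says why the whole-cohort figure suits it.

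**The concern.** In a single-arm trial the null median takes the place of the control arm. Here it is the only PFS comparator: the one planned comparison with patients on standard-of-care Keytruda (Sections 2.4.4 and 8.0) concerns stool microbiome and metabolites.

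The benchmark population contains a group that cannot enter this trial, and that group responded less than half as often as the PD-L1-positive group. If PD-L1-positive patients also stay progression-free longer on pembrolizumab alone, part of any gain over 2.0 months would come from selection. No planned analysis could separate that part from an effect of telatinib.

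**Working it through.** **1. The plan's own figure.** Inputs from Section 9.1: medians 2 and 4 months, two-sided 0.05, 80% power, uniform accrual over 12 months, 6 months of follow-up. Let λ0 = ln2/2, λ1 = ln2/4, O = observed events, E = events expected under the null.

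- Event probability under the alternative: p = 1 − (e^(−6λ1) − e^(−18λ1))/(12λ1) = 1 − (0.3536 − 0.0442)/2.079 = 0.851.
- Expected null events per patient: e = p × λ0/λ1 = 1.702.
- Drift: μ = p − e = −0.851.
- Variance of O − E per patient under the alternative: v = p + 2 × E[Λ²] − μ² = 0.851 + 2 × 1.184 − 0.725 = 2.494, where Λ is the cumulative hazard under the alternative at exit.
- n = (1.96√e + 0.8416√v)²/μ² = (2.557 + 1.329)²/0.725 = 20.85, so 21.

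The stated 21 reproduces with null variance E. With (O+E)/2 in place of E the formula gives 17.3, so 18. The plan does not state its variance form; both are shown below.

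**2. How mixed the benchmark was.** If PD-L1 status was known for nearly all patients, the negative share is (15.5 − 11.6)/(15.5 − 6.4) = 3.9/9.1, about 43%. This is inferred, not stated. Section 1.1.1 reports seven MSI-high tumours as 4%, a denominator near 7/0.04 = 175 rather than 259, so complete biomarker data cannot be presumed. It also does not state the PD-L1 cut-off behind the split.

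**3. What median that could imply.** The documents cannot answer this. Two illustrations, each with an assumption that they do not support:

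- Non-responder PFS does not depend on PD-L1, and only the responder share changes (11.6% to 15.5%). The PD-L1-positive median is then 2.08 months if responders have a median of 6 months, and 2.15 if they never progress.
- PFS is exponential in each group, 57% are positive, and the PD-L1-negative median is assumed. A negative median of 1.9, 1.8 or 1.5 months gives a positive median of 2.08, 2.17 or 2.52.

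**4. Consequence at n = 21.** Simulation with exponential PFS and the plan's accrual and follow-up; improvement is declared if Z < −1.96. The first two result columns are the chance of declaring improvement over 2.0 months with no telatinib effect, against a nominal 2.5%. The last two are power with variance E if the null is raised to the value in the first column.

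| Assumed pembrolizumab-alone median, CPS ≥1 | Declared, variance E | Declared, (O+E)/2 | Power, 4-month target kept | Power, HR 0.5 kept |
|---|---|---|---|---|
| 2.0 | 1.6% | 2.5% | 84% | 84% |
| 2.1 | 2.8% | 4.3% | 78% | 84% |
| 2.25 | 5.9% | 8.4% | 68% | 83% |
| 2.5 | 14.5% | 19% | 50% | 82% |

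**5. Size of a positive result.** Solving (O − E)/√E = −1.96 gives E = 32.1 at O = 21 and E = 26.0 at O = 16. The smallest estimated median that rejects 2.0 is 2 × E/O, which is 3.06 to 3.25 months. A benchmark shift to 2.1–2.25 months would therefore explain only part of a positive result.

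**The case against.** The best defence is that the benchmark matches on drug, dose and third-line-or-later setting, and that Kaplan-Meier curves with 95% bands are planned, so a reader can set the result against any other median. Both points are fair. But the curves do not change the formal null on which a claim of improvement would rest, and they cannot separate selection from drug effect.

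A second defence is that the effect is probably small: the responder-only illustration gives 2.08–2.15 months and, with variance E, an error of 2.5–3.6%. A reader might infer this, but it rests on the assumption that PD-L1 does not affect non-responders. No PFS data in the documents support that, and nothing caps the median at 2.15 or 2.25.

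A third is that other features of this trial may offset the bias. It admits "Eastern Cooperative Oncology Group (ECOG) performance score of 0, 1, or 2", and Section 2.4.1 counts clinical progression if it comes earlier. The documents do not give the benchmark's performance-status criteria or progression definition, so neither can be called a known difference.

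One objection stands in full. This is an open-label trial at protocol version 4, and changing the governing null is sound only if AGC outcome data have not yet been examined.

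**Conclusion.** The mismatch is documented and unexplained: a null from a PD-L1-mixed cohort is applied to a CPS ≥1 population in a trial with no concurrent PFS control. The size of the bias is unknown. The likely direction, a null that is too low, is inferred from response rates and not from PFS. Over an assumed range of 2.1 to 2.5 months the chance of a false claim runs from about 2.8% to 14.5% with variance E, the form that reproduces 21, or from 4.3% to 19% with (O+E)/2. These figures rest on exponential PFS and on the plan's accrual and follow-up.

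A reader might infer that the test's error rate is 15–19%, or that the sample size is wrong. Neither follows. The higher rates hold only if the true median is near 2.5 months, which the documents neither show nor exclude, and 21 is correct on its stated inputs. The defect lies in the benchmark, not in the arithmetic. The plan should be changed, but the design is not invalid.

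**What to change.** Amend the schema and Sections 9.1 and 9.3.1.

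1. **If no AGC outcome data have been examined:** set the AGC null to the median PFS of the PD-L1-positive subgroup of the same cited trial, and state that subgroup's PD-L1 cut-off. Restate power for the fixed 21 patients, saying whether the 4-month target or HR 0.5 is kept.
2. **If that figure is unavailable, or AGC outcome data have been examined:** keep 2.0 months as the governing null. Add a pre-specified sensitivity analysis reporting the one-sample log-rank result against the subgroup median or, failing that, against nulls of 2.1, 2.25 and 2.5 months. State that any claim of improvement will be qualified if it does not hold across that range.

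The cost is wording in three places and one recalculation, with no extra patients, visits or data. The price is a less favourable stated power (at a null of 2.25 with the 4-month target kept, 68% instead of 84%, variance E) or a more qualified conclusion. Matching on PD-L1 does not establish that the two populations are alike in other respects.

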9.3.2 Safety Analysis

All subjects who receive at least one dose of telatinib will be included in the safety analysis. The frequencies of AEs by type, body system, severity and relationship to study drug will be summarized. SAEs (if any) will be described in detail.

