5.2 Toxicities and Dosing Delays/Dose Modifications

Telatinib known toxicities include:

- Nausea, vomiting, and diarrhea: Antiemetics and antidiarrheal agents may be administered to prevent or control symptoms.
- Hypertension
- Fatigue
- Liver injury
- Proteinuria/renal injury
- Hand and foot syndrome: Symptomatic therapy may be provided if necessary.
- Hypokalemia: Potassium treatment should be given in the event of hypokalemia.
- Hemorrhage
- Gastrointestinal perforation
- Cardiac function abnormality

Please refer to the telatinib IB for more details.

Toxicities may be treated symptomatically per standard of care/investigator discretion. Telatinib administration may be held at the investigator's discretion for any reason. Dose modifications are permitted. Any dose holds or modifications will be documented in the research record.

Dose Modifications and Delays for Telatinib

General dose reductions for telatinib are outlined in the following table.

Dose Level	0	-1	-2
Telatinib	900 mg BID	600 mg BID	300 mg BID
	(3 tablets twice a day)	(2 tablets twice a day)	(1 tablet twice a day)

If a dose reduction of telatinib is required and the toxicity resolves and no additional toxicities are seen after 6 weeks of treatment at the reduced dose (2 cycles), then telatinib may be increased to the dose prior to the reduction, not to exceed the original dose of 900mg (3 tablets) BID.

Any clinical event that requires dose reduction must be recorded as an AE and recorded in the CRF. For any dose that is not administered according to the protocol, the reason for the omission must be recorded in the CRF.

Suggested Dose	• Modifications	for Telatinib-	Associated Toxicities
----------------	-----------------	----------------	-----------------------

Toxicity	Non-hematologic	Hematologic
Grade 1	 Continue at the same dose level 	 Continue at the same dose level
Grade 2	• Continue at the same dose level	• Continue at the same dose level
Grade 3*	 Withhold dose until toxicity is grade ≤2, then resume treatment at the same dose level. 	 Continue at the same dose level

	 If subject experiences a second grade 3 toxicity, withhold dose until toxicity is grade <1, then reduce 1 dose level and resume treatment 	

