Grade 4**	 Withhold dose until toxicity is grade ≤2, then reduce 1 dose level and resume treatment, or discontinue at the discretion of Investigator 	 Withhold dose until toxicity is grade ≤2, then reduce 1 dose level and resume treatment, or discontinue at the discretion Investigator

*Subjects who develop grade 3 fever/chills, grade 3 elevation of hepatic transaminases with ALT and AST <10X ULN, grade 3 hyperlipasemia or hyperamylasemia without clinical or other evidence of pancreatitis, grade 3 hypophosphatemia, grade 3 leukopenia, or grade 3 lymphopenia may continue telatinib without interruption at the discretion of the Investigator. NOTE: Refer to CTCAE v 5.0 for grade definitions.

**Subjects with grade 3 or 4 allergic reactions to telatinib should be removed from treatment. Subjects with grade 2 allergic reactions should be carefully assessed for potential risk of serious or life-threatening reactions following re-exposure to telatinib.

Pembrolizumab

Pembrolizumab toxicities and dosing delays/dose modifications will be managed per standard of care, the package insert, and investigator discretion. Pembrolizumab is associated with immune-related adverse events and infusion reactions. Please refer to the package insert for more details.

In the event that pembrolizumab is discontinued, treatment with telatinib may continue.

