7.1.1.1 Laboratory test abnormalities

A laboratory test abnormality considered clinically relevant (e.g., causing the subject to withdraw from the study, requiring treatment or causing apparent clinical manifestations, result in a delay or dose modification of study treatment, or judged relevant by the investigator), is considered an adverse event.

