7.2.1 AE Documentation

A laboratory test abnormality considered clinically relevant (e.g., causing the subject to withdraw from the study, requiring treatment or causing apparent clinical

manifestations, result in a delay or dose modification of study treatment, or judged relevant by the investigator), should be reported as an adverse event.

The investigator or sub-investigator (treating physician if applicable) will document the following for all adverse events (both serious and non-serious):

- Event term- according to the NCI Common Terminology Criteria for Adverse Events (CTCAE) version 5. The CTCAE current version is available at http://ctep.cancer.gov/reporting/ctc.html
- Description of the event
- Date of onset and resolution
- Expectedness of the toxicity
 - Expected events are those that have been previously identified as resulting from administration of the agent. An adverse event is considered unexpected, for expedited reporting purposes only, when either the type of event or the severity of the event is not listed in:
 - the current known adverse events listed in this protocol;
 - the drug package insert; and/or
 - the current Investigator's Brochure
- Grade of toxicity
 - Attribution of relatedness to the investigational agent- (this must be assigned by an Investigator, sub-investigator, or treating physician)
 - Attribution categories are as follows:
 - Definite: The AE is clearly related to the study treatment.
 - Probable: The AE is likely related to the study treatment.
 - Possible: The AE may be related to the study treatment.
 - Unlikely: The AE is doubtfully related to the study treatment.
 - Unrelated: The AE is clearly NOT related to the study treatment.
- Action taken as a result of the event, including but not limited to; no changes, dose interrupted, reduced, discontinued, etc. or action taken with regard to the event, i.e. no action, received conmed or other intervention, etc.
- Outcome of event

Source documentation must be available to support all AEs.

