7.2.2 Duration of AE monitoring

All patients experiencing an adverse event, regardless of its relationship to study drug, will be monitored until:

- the AE resolves or the symptoms or signs that constitute the AE return to baseline
- any abnormal laboratory value deemed an AE as per section 7.1.1.1, has returned to baseline
- there is a satisfactory explanation other than the study drug for the changes observed
- death, or
- until 30 days following last dose of study drug or until initiation of a new anticancer therapy (whichever occurs first)

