7.2.3 Pembrolizumab

As pembrolizumab is FDA-approved for this indication and used in accordance with the package insert, only events determined to be unexpected and at least possibly related to pembrolizumab will be recorded in the eCRF.

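### Expected events attributed to pembrolizumab need not enter the eCRF, and laboratory values count only if judged relevant, so the planned AE frequencies can understate the combination's toxicity

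*Combined protocol and SAP*

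**What the plan says.** Safety is a secondary objective (2.2.4), and its endpoint is the incidence and CTCAE v5 severity of AEs (2.4.3). Section 9.3.2 states that "The frequencies of AEs by type, body system, severity and relationship to study drug will be summarized" and adds that SAEs will be described. It names no table of measured laboratory values.

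Two rules decide which events reach those frequencies.

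- **Pembrolizumab events.** Section 7.2.3 reasons that the drug is approved and used according to its package insert, and so "only events determined to be unexpected and at least possibly related to pembrolizumab will be recorded in the eCRF".
- **Laboratory values.** Section 7.1.1.1 makes an AE of "A laboratory test abnormality considered clinically relevant (e.g., causing the subject to withdraw from the study, requiring treatment or causing apparent clinical manifestations", with delay or modification of study treatment and investigator judgement as further examples. Section 7.2.1 repeats the test, ending "or judged relevant by the investigator), should be reported as an adverse event". Section 7.2.2 follows up "any abnormal laboratory value deemed an AE as per section 7.1.1.1, has returned to baseline", so values not deemed AEs are outside that follow-up.

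In 5.2, the entry for grade 3 hematologic toxicity in the table of suggested telatinib modifications is "Continue at the same dose level". The default for grade 3 non-hematologic toxicity is to withhold. A footnote lists exceptions, among them "grade 3 elevation of hepatic transaminases with ALT and AST <10X ULN", and ends: "grade 3 leukopenia, or grade 3 lymphopenia may continue telatinib without interruption at the discretion of the Investigator".

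Other text points the other way. Section 6.1.6 has the details of AEs, including grade and relation to study drug, go onto the CRF. Section 7.2.1 requires documentation of every AE, serious or not. Section 7.2 sends AEs to the medical record.

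**The concern.** The trial tests a combination, and its safety result is meant to describe that combination. An event that is expected for pembrolizumab alone may still occur more often, or at a higher grade, when telatinib is added. A rule that keeps such events out of the eCRF removes the data needed to see this.

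The liver is where it matters most. Liver injury is a listed telatinib toxicity (5.2), and the protocol's own account of pembrolizumab in HCC names raised AST and ALT among its common treatment-related events (1.1.2). Both drugs can therefore raise the same enzymes, and in a single-arm trial the attribution of a given rise is uncertain. Under 7.2.3 that uncertain judgement can decide whether the event is entered at all.

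The relevance test adds a second, softer filter on laboratory toxicity, although chemistry and hematology are drawn before every cycle.

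**Working it through.** The plan gives no figure for event capture, so there is nothing to reproduce. The check is a reading of the rules, followed by the weight of one patient.

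**Step 1. What is reported.** Section 9.3.2 gives AE frequencies and SAE descriptions. Section 9.3.1 plans confidence intervals for changes in biomarkers such as cytokines and plasma metabolites, not for routine chemistry or hematology. No worst-grade or shift table appears in section 9.

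**Step 2. The pembrolizumab route.**

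| Event | Reaches the AE frequencies? |
|---|---|
| Attributed to telatinib, alone or with pembrolizumab | Should be recorded; 7.2.3 concerns pembrolizumab events |
| Attributed to pembrolizumab only, unexpected | Yes, under 7.2.3 |
| Attributed to pembrolizumab only, expected | No under 7.2.3; yes if 6.1.6 and 7.2.1 are taken to govern |

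The third row is the gap. It does not depend on grade or on whether the event is a laboratory finding. Nothing in the protocol says which rule prevails. The medical record under 7.2 would hold the event, but 9.3.2 does not plan to tabulate from charts.

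**Step 3. The relevance route.** No CTCAE grade qualifies a laboratory value as an AE by itself. Take a grade 3 ALT below 10 times ULN, or a grade 3 neutrophil count, in a patient without symptoms or treatment for it. Under 5.2 telatinib may continue, so the dose-action example need not apply. If pembrolizumab is not held either, the value counts only if the investigator judges it relevant. Grade 1 and 2 values face the same test.

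**Step 4. Direction.** Each route can remove an event from the count, and neither can add one. Any error from them is an understatement.

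**Step 5. Size.** The number of patients omitted, k, cannot be derived from the documents. The cohort sizes in 9.1 are 21 (gastric) and 24 (HCC), and the effect on a reported incidence is k/N:

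- k = 0: no effect in either cohort.
- k = 1: 1/21 = 4.76, or 4.8 percentage points; 1/24 = 4.17, or 4.2 points.
- k = 2: 2/21 = 9.5 points; 2/24 = 8.3 points.

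The values of k are assumptions that show scale, not estimates.

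**The case against.** The strongest reply is that plan and endpoint agree: the endpoint is AEs, and AEs are what 9.3.2 counts. A laboratory value that is not an AE lies outside the endpoint, and its absence is not an error. The relevance definition is also open-ended, since it lists examples and ends with investigator judgement, so every grade 3 value may be recorded. This largely stands for the relevance route, which shows that omission is possible, not that it is likely. It does not answer 7.2.3, which can keep out events that are AEs by the protocol's own definition.

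It is also fair that 7.2.3 takes effect only when an event is attributed to pembrolizumab and not to telatinib, and is judged expected. Section 7.2.1 defines expectedness for expedited reporting only, by reference to the protocol, the package insert and the investigator's brochure. The last two are not available here, so how a grade 3 transaminase rise would be classed cannot be settled.

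A reader might multiply the 7% AST and 4% ALT rates quoted for the HCC reference trial by 24, giving 1.7 and 1.0 patients, and call that the loss. The documents do not support this. Those are AE rates, already recorded, from pembrolizumab alone in another trial; they say nothing about how many events would go unrecorded here.

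In the other direction, a reader might infer that grade 4 values are always captured because 5.2 withholds telatinib for them. That does not follow either. The table is headed as a suggestion, and an expected grade 4 event attributed to pembrolizumab alone meets the same 7.2.3 restriction.

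**Conclusion.** The point holds as a one-directional risk to a secondary endpoint. As written, 7.2.3 can keep expected pembrolizumab-attributed events of any grade out of the planned AE frequencies, and it conflicts with 6.1.6 and 7.2.1. The clinical-relevance test is a secondary route for laboratory values. The size is unknown and may be zero; each omitted patient is worth 4.8 points in the gastric cohort or 4.2 in HCC. This rests on 7.2.3 being applied literally, on attribution to pembrolizumab alone, and, for the second route, on investigators leaving some values unrecorded.

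It would go too far to infer that toxicity will be understated, or that the efficacy analysis or the safety stopping rule is compromised. PFS does not depend on AE recording. The stopping rule counts only telatinib-related SAEs and deliberately leaves out those due to pembrolizumab alone (5.2.1). All SAEs go to the principal investigator whatever their attribution (7.3.1.1), and the DSMC reviews the study (10.5.2). The change is worth considering because it is cheap, not because a planned decision turns on it.

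**What to change.** Add to 9.3.2:

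> For each cohort, in every patient who took any telatinib, CTCAE v5 grades will be derived from the scheduled ALT, AST, bilirubin, creatinine and hematology values. Baseline grade will be tabulated against worst on-treatment grade, whatever the AE status or attribution. The number of patients at grade 3 or higher will be shown beside the corresponding AE count. Differences may reflect the clinical-relevance judgement (7.1.1.1) or the pembrolizumab recording rule (7.2.3).

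The panels are already drawn at screening, before each cycle and 30 days after treatment (6.1.8, 6.2.1, 6.2.4), so no test or visit is added. The cost is one paragraph, one or two programmed tables per cohort, and data entry if laboratory values are not already in the study database.

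The table will also include abnormalities due to underlying or progressing liver disease. Entry allows ALT and AST up to 5 times ULN with liver metastasis (3 times without) and bilirubin up to 3 times ULN (4.1.6). The baseline comparison helps, but only in part.

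The table cannot recover non-laboratory events excluded by 7.2.3, such as rash, diarrhea or colitis; that would need 7.2.3 itself changed so that all AEs on the combination are entered, at the price of more data entry. Nor can it recover lipase, amylase or phosphate, which the 5.2 footnote covers but the scheduled panel does not include.
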